### **6.1.1 Administration of Intervention**

Referral to Homebase will be provided in-person by study staff as detailed above during the study baseline ED visit. Participants will be encouraged by study staff to visit the appropriate Homebase office within one week from the time of their baseline visit; some Homebase offices may accept appointments and others operate on a walk-in basis. Homebase services are generally provided in-person at the Homebase offices, though some services may also be provided by staff over the phone. The frequency, mode, and duration of contact with Homebase will be determined by the participant and Homebase staff, and is likely to vary depending on individuals' needs.

Referral to substance use services will be provided in-person by study staff as detailed above. The SBIRT and Addiction Leads teams will provide services as detailed above in-person during the baseline ED visit. Follow-up services will depend on the individual needs of the participant and may include follow-up phone calls to check on progress. Participants may also be referred to other services, such as outpatient clinics for substance use or inpatient substance use treatment programs. The exact services, timing, frequency, mode, and duration will depend on individual participant needs.

Follow-up by study staff to ensure that participants receive needed services will occur by phone. Study staff will talk with participants to help facilitate service receipt by phone up to three times, using the schedule as outlined in the Schematic of Study Design Section (Follow-Up Procedures Flow Chart). In the cases where participants aren't able to be reached by phone and where they have given us permission to email them, we may also use a study NYULH SendSafe email to contact the participant. Additionally, if we are unable to reach the participant, and the participant has given us permission to do so, we may contact the participant's place of work, health care providers, case workers/social workers, or substance use treatment programs that they attend. Study staff will also communicate with staff from Homebase and the NYC Department of Social Services as needed to facilitate referrals.

### CONFIDENTIAL

## 6.1.2 Procedures for Training Interventionalists and Monitoring Intervention Fidelity

ED-Home study staff will be trained in making referrals to Homebase, SBIRT, and Addiction Leads services. Study staff will also be trained in the protocol for making follow-up phone calls to help ensure that participants receive needed services. Details on all referrals at the time of baseline and all follow-up phone calls will be documented in REDCap, which will allow for monitoring of adherence to study procedures.

As this is a real-world intervention utilizing referrals to existing social and substance use services operated by entities separate from the ED-Home study, study staff will not have a role in training, monitoring, or supervising the staff providing Homebase, SBIRT, Addiction Leads, or other interventions. Study staff will be able to obtain limited information from study participants during baseline and six-month follow-up interviews about what services they were able to receive and their satisfaction with those services. As detailed above, study staff will also receive information from Homebase about the status of referrals that have been made. Other information about service receipt will be obtained as part of measuring the feasibility of the study, as outlined in other sections of the protocol.

## 6.1.3 Assessment of Subject Compliance with Study Intervention

We will ascertain in follow-up phone calls and at the time of the 6 month follow-up survey what services participants have received as a result of study intervention referrals, and the results of those referrals. This information will be based primarily on participant self-report, with additional information obtained from Homebase staff as needed.

# 7 Study Procedures and Schedule

## 7.1 Study Procedures/Evaluations

### 7.1.1 Study Specific Procedures

Study procedures are outlined in the two flow charts in the Schematic of Study Design section. These procedures include:

- Screening for study eligibility, informed consent process for eligible and interested patients (baseline).
  - For patients who may be homeless or at risk for homelessness but not eligible for the study, RAs will offer the patient a resource sheet (see *Housing Resource Sheet*).
- Survey (to be administered at baseline and 6 month follow-up visits): verbally administered survey to collect participant satisfaction information on intervention components and participant information including sociodemographics, physical and mental health, housing history, substance use history, criminal justice history, social support and social determinants of health. See specific instruments (attachments) for details:
  - *ED-Home Baseline Screening and Survey* (to be administered on REDCap)
  - *ED-Home 6 Month Follow-Up Survey* (to be administered on REDCap)
    - As part of the *ED-Home 6 Month Follow-Up Survey*, we will show participants the *Housing Risk Flyer* (administered on paper) which highlights certain risk factors for losing housing. We will then ask participants a series of questions about what they thought of the flyer.
    - As part of the *ED-Home 6 Month Follow-Up Survey*, we will show participants a NYC HRA YouTube video (administered on YouTube on study iPad) about a woman who successfully connected to Homebase. We will then ask participants a series of questions about what they thought of the video.
  - *Additional Baseline and Follow-up Questionnaires administered on paper*: alcohol timeline follow-back; residential timeline follow-back; WHO-ASSIST.
- Participant information form (baseline only): collects name, date of birth, SSN (if applicable) to allow future linkage with NYC DSS CARES database and Bellevue Hospital medical records (*ED-Home Participant Information Form*).
- Intervention (begins at baseline): detailed in Section 6.1. Includes:
  - Homebase referral (baseline only): contains participant basic information and is e-mailed

CONFIDENTIAL

- to the appropriate Homebase office (*ED-Home Homebase Referral Form for Bellevue Pilot*)
- Homebase information sheet (baseline only): contains name, location, hours, and contact information for the appropriate Homebase office as well as information about Homebase. This referral information will be given to the participants (*ED-Home Homebase Information Sheet*).
- SBIRT (Screening, Brief Intervention, and Referral to Treatment) and/or Addiction Leads services for substance use in ED (as detailed in Section 6)
- Locator form (baseline only): collects detailed contact information from participants to allow for future follow-up (*ED-Home Locator Form*).
- Study contact card and sticker (baseline only): serves as a reminder for the participant's 6 month follow-up visit and contains study staff information to allow participants to contact study staff proactively as needed (*ED-Home Study Contact Card and Sticker*).
- Follow-up phone calls to confirm participant contact information, confirm follow-up appointment, and reschedule missed visits (see ED-Home Follow-Up Procedures Flow Chart in Schematic of Study Design section), documented in REDCap (*ED-Home Tracking Form* and *ED-Home Follow-up Procedures Form*) and tracked using an Excel tracking log for internal study management purposes.
- Follow-up phone calls and/or NYULH SendSafe emails with participants and service providers (e.g., Homebase) to confirm referrals successful and troubleshoot as needed (see ED-Home Follow-Up Procedures Flow Chart in Schematic of Study Design section), documented in REDCap (*ED-Home Tracking Form* and *ED-Home Follow-up Procedures Form*) and tracked using an Excel tracking log for internal study management purposes.
- Mailing a follow-up visit reminder letter containing details of the participant's appointment, documented in REDCap (*ED-Home Follow-up Visit Reminder Letter* and *ED-Home Follow-up Procedures Form*).
- Electronic medical record review for Bellevue Hospital to ascertain information on ED visits, inpatient hospitalizations, outpatient visits, and substance use service visits at Bellevue Hospital (*ED-Home EMR Data Abstraction Tool*).
- Via NYC governmental agencies (NYC Department of Social Services and/or NYC CIDI), review of CARES database (with consent of participants) for data on participants' homeless shelter use, including dates and types of shelter use prior and subsequent to study enrollment. NYC DSS—which administers the Homebase program to which we are referring participants as part of the intervention—has agreed to inform us of the outcomes of our referrals (either directly or via their contracted agencies), including whether the participants enter a homeless shelter, for participants who have provided consent. NYULH researchers will not be directly accessing outside databases.

### 7.1.2 Standard of Care Study Procedures

The study will not interfere with the standard clinical care that patients receive while in the ED. The referral to substance use services (SBIRT and Addiction Leads) are part of standard care offered in the ED during times in which these programs operate. In general, SBIRT and Addiction Leads staff actively screen patients in the ED to identify patients in need of their services. In addition, clinical staff (e.g., nurses, physicians) can refer patients to SBIRT and Addiction Leads programs based on their clinical judgment of need. The SBIRT and Addiction Leads services that will be offered to study participants are the same as those offered as part of routine clinical care; the only difference is that for the study our study staff will facilitate real-time referrals for participants to ensure that participants receive these ED-based services. Therefore, any referrals, treatments (including assistance in obtaining medication treatment), or other services provided as part of SBIRT or Addiction Leads referrals will be considered to be part of standard of care in the ED, not unique services offered through the study.

Other referrals as part of the study (e.g., to Homebase) are not currently part of routine/standard of care in the ED, though currently ED care providers refer patients to social workers on an *ad hoc* basis as needed to assist with housing and homelessness concerns. Our study referral to Homebase represents an enhancement in the standard of care since currently social work services in the ED for housing/homelessness are quite limited in scope.

#### CONFIDENTIAL

## **7.2 Laboratory Procedures/Evaluations**

Not applicable.

## **7.3 Study Schedule**

Full details on the study schedule, including all baseline and follow-up procedures, are provided in the Schematic of Study Design figures presented near the beginning of this protocol.

### **7.3.1 Screening**

Screening for study eligibility will occur during a patient's Bellevue Hospital ED visit. The process for screening is provided in the *ED-Home Pilot Baseline Procedures* flow chart in the Study Schema section of this protocol. The process for screening is fully described in protocol Section 5.4 and the attachment *ED-Home Baseline Screening and Survey*.

### **7.3.2 Enrollment/Baseline**

The baseline/enrollment visit will occur during the same ED visit as screening. All baseline procedures will occur during this visit. Research staff will confirm eligibility for the study by reviewing the screening information collected by RAs and affirming accuracy with participants. The sequence of baseline visit events is outlined in the ED-Home Pilot Baseline Flow Chart in the Study Schema section.

#### **Enrollment/Baseline Visit (Visit 1, Day 0)**

- Verify inclusion/exclusion criteria.
  - If patient may be homeless or at risk for homelessness but not eligible for the study, give homelessness resource sheet.
- Verify patient has not already participated in the study.
- Explain the study. Obtain informed consent of potential participant verified by signature on study informed consent form. One copy of completed informed consent form will be given to participant and the other copy retained for study records.
- Complete baseline survey and supplemental questionnaires (see instruments as listed in Section 7.1.1).
- Complete participant information form (see Section 7.1.1).
- Real-time referral to substance use services to be provided during baseline visit (SBIRT and/or Addiction Leads).
- Referral for Homebase homelessness prevention services.
- Complete Participant Locator Form (see Section 7.1.1).
- Schedule follow-up appointment and give appointment using study contact card and sticker.
- Participant given \$30 baseline reimbursement and one round-trip regular MetroCard.

### **7.3.3 Intermediate Visits**

Intermediate "visits" will occur via phone as outlined in the ED-Home Follow-Up Procedures Flow Chart in the Study Schema section. In the cases where participants aren't able to be reached by phone and where they have given us permission to email them, we may also use a study NYULH SendSafe email to contact the participant. Additionally, only if we are unable to reach the participant directly and if the participant has given us permission to do so, we may contact the participant's place of work, health care providers, case workers/social workers, or substance use treatment programs that they attend by phone. The purpose of these contacts is solely to assist us in getting in contact with the participant to minimize loss from the study (e.g., obtaining from these secondary contacts any new phone number information the participant may have); we will not be sharing any information about the study or the participants with these contacts. The timeline provided is suggested, but exact dates may deviate depending on circumstances such as how difficult it is to contact the participant. Strict time windows will not be mandated for intermediate contacts, though all attempts will be made for these contacts to occur with timing as close to that outlined in the flow chart as possible. This is appropriate for a feasibility study and dates of all follow-up contacts and attempts at contacts will be recorded on REDCap (see *ED-Home Tracking Form*) and a summary Excel tracking

CONFIDENTIAL

spreadsheet that will be used internally to manage participant status, attempts of contact with participants, attempts of contact with providers, and necessary follow-up steps; no protected health information will be recorded on the Excel tracking log.

**Intermediate Contact 1 (Day 7–10)**

- Confirm participant contact information.
- Confirm 6 month follow-up visit date.
- Ascertain whether referrals successful. If unsuccessful troubleshoot and decide next steps.

**Intermediate Contact 1.2 (as needed, 7–10 days after Intermediate Contact 1)**

- Only for participants in whom referrals were unsuccessful.
- Ascertain whether participant received services to which referred. If unsuccessful troubleshoot and decide next steps.

**Intermediate Contact 1.3 (as needed, 7–10 days after Intermediate Contact 1.2)**

- Only for participants in whom referrals were unsuccessful.
- Ascertain whether participant received services to which referred. If unsuccessful troubleshoot and decide next steps.

**Intermediate Contact 2 (3 months after baseline)**

- Confirm participant contact information.
- Confirm 6 month follow-up visit date.

**Intermediate Contact 3 (5 months after baseline)**

- Confirm participant contact information.
- Confirm 6 month follow-up visit date.
- Mail participant 6-month follow-up visit reminder letter.

**7.3.4 Final Study Visit**

The final study visit will be the 6 month follow-up visit. The procedure for participants who do not come to the follow-up visit is documented in the ED-Home Follow-Up Procedures Flow Chart in the Study Schematic Section.

***Final Study Visit (6 months, window -2 weeks to +8 weeks)***

- Complete 6 month follow-up survey (see instruments as listed in Section 7.1.1).
- Participant is reminded that this is the final study visit. Participant is thanked for his/her time and has the opportunity to ask any questions about the study.
- Participant given \$50 (cash or gift-card) follow-up reimbursement.

**7.3.5 Withdrawal Visit**

Participants may choose to withdraw from the study by informing the PI in writing or by phone. There will not be a separate withdrawal visit. See Section 5.7 for additional details.

**7.3.6 Unscheduled Visit**

Unscheduled visits are not anticipated. Participants will be given contact information for the study to inform us of any change in their contact information. If the participant makes such contact it will be documented in the follow-up log in REDCap.

**7.4 Concomitant Medications, Treatments, and Procedures**

Not applicable.

**7.5 Justification for Sensitive Procedures**

Not applicable.

CONFIDENTIAL

### 7.5.1 Precautionary Medications, Treatments, and Procedures

Not applicable.

### 7.6 Prohibited Medications, Treatments, and Procedures

Not applicable.

### 7.7 Prophylactic Medications, Treatments, and Procedures

Not applicable.

### 7.8 Participant Access to Study Intervention at Study Closure

Participants will still be able to access all existing community/social services for which they are eligible and ED/health care at the end of the study as they would if they had not participated in the study.

## 8 Assessment of Safety

### 8.1 Specification of Safety Parameters

This is an extremely low-risk study given the nature of the intervention (referrals to established social services). As such, study endpoints do not include safety parameters. Since the study includes participants with social and medical risks including housing instability and homelessness, we expect that some participants will worsen in status during the course of the study unrelated to the study. Though we will document and respond to any adverse events that we become aware of during the study as described below, we are not performing explicit investigations to attempt to discover adverse events since such events are not expected related to the study. For example, we are not tracking diagnostic test results. We are not tracking hospital stays in real-time. Information about hospitalizations will be recorded retrospectively as an exploratory study outcome as previously described, but such stays will not be considered adverse events.

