#### 8.1.2 Definition of Serious Adverse Events (SAE)

##### Serious Adverse Event

*Required text:* Adverse events are classified as serious or non-serious. A **serious adverse event** is any AE that is:

- fatal
- life-threatening

CONFIDENTIAL

- requires or prolongs hospital stay
- results in persistent or significant disability or incapacity
- a congenital anomaly or birth defect
- an important medical event

Important medical events are those that may not be immediately life threatening, but are clearly of major clinical significance. They may jeopardize the subject, and may require intervention to prevent one of the other serious outcomes noted above. For example, drug overdose or abuse, a seizure that did not result in in-patient hospitalization, or intensive treatment of bronchospasm in an emergency department would typically be considered serious.

All adverse events that do not meet any of the criteria for serious should be regarded as **non-serious adverse events**.

*Study specific text:* Given the population being enrolled in the study, it is expected that most participants will continue to have substance use (drug and alcohol), several may have overdose, and many may have hospitalizations or other treatments related to their substance use. These outcomes are being included in the 6 month follow-up assessment for exploratory analyses. When we learn about these outcomes at the time of follow-up assessments they will not be considered AEs/SAEs, but rather will be analyzed as for other exploratory study outcomes. We do not expect to learn about these outcomes in the interim (during the study before the 6 month follow-up visit) because we are not actively tracking participants' clinical status or health care use.

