### 8.2.2 Relationship to Study Intervention

All events considered to be AEs will have their relationship to the study intervention/study participation assessed by the study PI, with consultation from the IRB, study sponsor, and/or study DSMB as appropriate. Determinations will be made based on factors including considerations of causality based on temporal relationships and clinical judgment. The degree of certainty about causality will be graded using the categories below:

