### 8.4 Reporting Procedures – Notifying the IRB

The PI will report the following types of events to the IRB and DSMB:

- AE or SAE AND unanticipated AND possibly, probably, or definitely related to the study. Study-specific descriptions of what will and will not be considered AEs or SAEs are provided in Sections 8.1.1 and 8.1.2.
- Anticipated adverse events occurring with greater frequency than expected.
- Knowledge of any death of a study participant, even if determined unrelated to the study.
- Other unanticipated problems involving risks to study participants or others.

These events will be reported according to the NYU Langone Health IRB's reporting guidelines.

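### Sections 8.1, 8.1.1 and 8.1.2 disagree on which hospital stays and substance-use events are adverse events, and these exclusions apply before relatedness is assessed

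*Combined protocol and SAP*

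**What the plan says.** The rules are spread over six sections of the protocol.

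- **8.1 (Specification of Safety Parameters).** "Information about hospitalizations will be recorded retrospectively as an exploratory study outcome as previously described", and the sentence ends "but such stays will not be considered adverse events". No cause is named, so all recorded stays are covered.
- **8.1.1 (Definition of AE).** Intercurrent illnesses and injuries count as AEs. The study-specific text then removes mild and moderate events if they are unrelated. It also removes a list of substance-use events, including medical events directly due to substance use, with no condition on relatedness or on when the event is learned of.
- **8.1.2 (Definition of SAE).** An AE is serious if, among other criteria, it "requires or prolongs hospital stay". Examples of important medical events include "drug overdose or abuse, a seizure that did not result in in-patient hospitalization". The study-specific text expects that several participants may overdose and that "many may have hospitalizations or other treatments related to their substance use". It then says: "When we learn about these outcomes at the time of follow-up assessments they will not be considered AEs/SAEs".
- **8.2.2 (Relationship to Study Intervention).** "All events considered to be AEs will have their relationship to the study intervention/study participation assessed by the study PI".
- **8.4 (Notifying the IRB).** The PI reports to the IRB and DSMB unanticipated AEs and SAEs that are at least possibly related, all known deaths, other unanticipated problems, and "Anticipated adverse events occurring with greater frequency than expected". For what counts as an AE or SAE, it refers to 8.1.1 and 8.1.2.
- **8.5 (Notifying the Study Sponsor).** At least possibly related AEs go to the funder at least yearly, and related SAEs within 72 hours. If there were no AEs, a statement to that effect is sent.

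**The concern.** Two faults are involved. The first is a contradiction of scope and timing: staff who record the same admission, or hear of the same overdose, will classify it differently depending on which section they follow.

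The second is the order of steps. An event that is not considered an AE has no required relatedness assessment. For hospital stays and substance-use events, the exclusion depends on the type of event and not on a judgement that the study played no part. Substance use is one of the two targets of the intervention (Section 6.1), so a harm of the intervention, if there were one, could plausibly appear there.

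At stake is what the pilot can say about safety. Section 2.2 says it will inform a larger trial, and its safety rules may be carried over. A statement that no related events occurred should rest on events that somebody looked at.

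**Working it through.** The protocol states no safety figure and the point rests on no calculation. The check is to take each kind of event through the sections in turn.

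1. **Hospital stay not due to substance use (for example a severe injury), recorded at 6 months.**
   - 8.1: not an AE.
   - 8.1.1: the injury is an AE. It is severe, so the mild and moderate exclusions do not apply.
   - 8.1.2: serious, under "requires or prolongs hospital stay". The study-specific exemption does not reach it, because that exemption concerns substance-related outcomes.
   - Result: two classifications for one event.

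2. **Substance-related stay or non-fatal overdose, learned at the 6-month assessment.**
   - 8.1 (for stays), 8.1.1 and the study-specific text of 8.1.2 agree that it is not handled as an AE or SAE.
   - There is no conflict of scope, but 8.2.2 is never reached.
   - The unanticipated-problem route in 8.1.3 has its own relatedness criterion and does not need AE status. It does require that the event be unexpected, and events expected in the eligible population do not qualify. Since 8.1.2 names these outcomes as expected, the route is largely closed. An unusual severity or frequency could still open it.
   - Result: a possibly related event can go unassessed.

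3. **The same event, disclosed at an interim contact.**
   - 8.1.1 excludes it whenever it is learned.
   - The 8.1.2 exemption is tied to follow-up assessments, and its next sentence treats the time before the 6-month visit as a separate case.
   - The general text of 8.1.2 lists overdose as typically serious.
   - 8.1.2 does not expect such news in the interim, but Section 7.3.3 plans calls at 7–10 days, up to two more as needed, and at 3 and 5 months. An expectation is not a rule for what to do when a participant volunteers it.
   - Result: excluded by one section and not exempted by the other.

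4. **Mild or moderate event outside substance use and without a hospital stay.** It is excluded only if unrelated, so relatedness must be judged first. The order is right here, which shows that the condition can be written.

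5. **Death.** Reported to the IRB and DSMB whatever the cause.

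6. **Unexpected, possibly related problem of any kind.** Reported under 8.1.3 and 8.4.3, whether or not it is an AE.

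Downstream, 8.5 reports only AEs and SAEs judged at least possibly related. An event in group 2, or in group 3 if 8.1.1 is followed, is absent from that report because the question was not asked. If no other AEs are on record, the funder would receive a statement that none occurred.

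**The case against.** The strongest reply is that hospitalization is a property of an AE and not itself an AE. On that reading, 8.1 removes only the stay, and the underlying illness remains an AE under 8.1.1. The reference in 8.4 to 8.1.1 and 8.1.2 alone also suggests that the sentence in 8.1 was not meant as an operative rule. The text allows this reading but does not state it, so the wording still has to be settled. It would not help with groups 2 and 3.

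It is also fair that light safety tracking is a deliberate, explained choice for a pilot built on referrals to existing services. That justifies little reporting, but not conflicting definitions.

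Several stronger inferences are tempting, and the documents do not support them:

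- *That every exclusion comes before the relatedness judgement.* The mild and moderate exclusions require that judgement first.
- *That a related event can never surface.* Deaths and unexpected, possibly related problems are reported regardless of AE status.
- *That these events are not counted and the DSMB has nothing to review.* Hospitalizations are abstracted from the Bellevue record (7.1.1), overdose and hospitalization are part of the 6-month assessment (8.1.2), both sources enter the analysis dataset (10.3), and the DSMB reviews study data yearly (8.8). What is missing is a specified safety table and a relatedness judgement for these events.
- *That the excess-frequency trigger in 8.4 is inoperative.* The anticipated risks in 2.3.1 (discomfort, fear about care, loss of confidentiality) are not defined away and could fire it. It is true only that no expected frequency is given and that the trigger's application to excluded events is unclear.

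**Conclusion.** The point holds in a limited form. For stays unrelated to substance use, 8.1 conflicts with 8.1.1 and 8.1.2. For substance-use events learned at interim contacts, 8.1.1 conflicts with the timing limit in 8.1.2. For hospital stays and substance-use events generally, the exclusion has no relatedness condition and comes before 8.2.2. The practical gap is confined mainly to possibly related, non-fatal overdoses and substance-related stays, which can miss both the relatedness assessment and the related-event report to the funder.

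Its size in events cannot be stated. The protocol gives no expected rate of stays or overdoses for its approximately 40 participants, only that several may overdose and many may be hospitalized. The conclusion does not depend on any rate. It assumes that staff follow the sections as written and that the 8.1 sentence is meant to apply to the event and not only to the stay. If the sponsor confirms the narrower meaning, the conflict over other stays becomes a matter of wording, and the order-of-steps gap for substance-use events remains. This should be corrected, but it does not threaten the feasibility endpoints.

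**What to change.** - Reconcile 8.1, 8.1.1 and 8.1.2 into one rule that says which stays and substance-use events are covered and whether the time of learning of them matters.
- Have the PI record relatedness, on the existing 8.2.2 scale, for any hospital stay, overdose or substance-use event that the study learns of, before an exclusion is applied. Limit the exclusion to events judged unrelated, and say which grades of the scale that means.
- Include counts of deaths, overdoses and hospital stays, with relatedness, in the yearly DSMB report. Draw them from the follow-up survey and the Bellevue chart review already planned, and note that the chart review sees only that hospital.
- State which events the excess-frequency trigger in 8.4 covers.

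The cost is protocol wording, one added field, slight extra PI time and a small table. No new data source is needed.
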